9.2 Sampling

9.2.1 Size of sample

a) Quantitative study

A total of 638 children and young people will be recruited to the study. This target is based on recruiting 70% of anticipated referrals to the GID service of children and young people age 13 years or under over an 18 month period. Of an estimated total of 3,298 referrals to the service in 18 months, 912 referrals pertained to children and young people aged 13 years or younger in 2016-2017. Allowing for 20% attrition and assuming 40% prevalence of GD (29) a total of 204 GD events are expected to be observed in the 510 children with complete follow-up in the cohort study. This will allow us to fit a logistic regression model with the 14 explanatory variables and estimate the resulting 19 regression coefficients with adequate precision (30). The sample size of 510 will also allow us to estimate the proportion of children with GD, expected to be 40% with reasonable precision 95% CI (35.75% to 44.25%). The proportion receiving physical intervention is anticipated to be around 21% during the follow up time and this proportion can be estimated with a 95% CI (17.45% to 24.55%) (31).

b) Qualitative study

We will purposively sample a sub-set of up to 40 families (children and young people and parents) from the quantitative study for the qualitative baseline interviews. We anticipate that a sample of this size will be necessary to achieve data saturation within sub-samples of interest, particularly to include children and young people who continue to experience gender dysphoria and progress to physical

treatments, as well as to include those who do not progress to physical treatments. Sampling to the qualitative study baseline interviews will cease when saturation and adequate information power (32) is judged to have been reached.

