3.1 Objectives

Our objective is to undertake a prospective longitudinal study of children and young people aged 3-13 years at the time of referral acceptance to the UK's GID service, consisting of both:

- 1. quantitative assessments at baseline and at yearly follow-up over two years;
- 2. qualitative interviews with both those referred and their caregivers, at baseline and at yearly follow-up over two years in a sub-sample of 40

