9.1.1 Inclusion criteria

In order for children and young people to take part in the study, they must:

- Be aged 3-13 years at the time referral was accepted;
- Have been referred to the GIDS and awaiting their initial appointment prior to first contact;
- Have parental consent;
- Speak English;
- Live in the UK.

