9.2.2 Sampling technique

a) Quantitative study

All children and young people aged 3-13 years when their referral was accepted by the GID service and awaiting a first appointment will be invited to participate in the study. This includes those currently sitting on the waiting list (n=585) and consecutive new referrals to the service (n~43 p/m) across the 18 month recruitment period. The waiting period will be divided into thirds and research effort equally extended on each third. In this way, we shall strive to treat each interval of waiting equally. Our revised strategy will be reviewed regularly and adapted should there be any change in policy towards, or service throughput of, this age group.

b) Qualitative study

Purposive sampling to the qualitative study will be informed by data from the quantitative study. A key aim is to interview CYP who subsequently go on to experience continuing gender dysphoria and progress to physical treatments, as well as CYP whose gender identity issues subsequently resolve and who do not progress to physical treatments. As these outcomes will not be known at baseline, sampling will take account of factors considered to be associated with these outcomes based on current research evidence and clinical knowledge. To address this we will sample equal numbers of CYP who have socially transitioned at baseline and equal numbers who have not socially transitioned at baseline, although we will review this strategy in the light of new evidence emerging over the course of baseline sampling. Across the whole sample we will aim to interview approximately 12 CYP with co-occurring ASD reflecting the large numbers of such CYP referred to GIDS, and approximately 6-8 black and ethnic minority CYP reflecting the UK general population. Sampling will also aim for balance in family socioeconomic status, location of GIDS and assigned gender at birth. Sampling will also be informed by the ongoing analysis of both the quantitative study data and qualitative data on an iterative basis.

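### The two-year clock for physical treatment starts on the waiting list, so time available for treatment after first appointment differs between children by design and the planned 21% has no stated time origin

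*Protocol*

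**What the plan says.** Research question 2 (Protocol, Section 3) asks what proportion of referred children go on to physical treatment and what predicts it. Section 2 treats this as a key question for the NHS.

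- **Entry.** Section 9.1.1 requires children to "Have been referred to the GIDS and awaiting their initial appointment prior to first contact". Sections 9.2.2 and 9.3.1 likewise draw the sample from children not yet seen.
- **Clock.** Section 3.1 sets "quantitative assessments at baseline and at yearly follow-up over two years". Section 5 and the Study Summary agree.
- **Recruitment.** Section 9.2.2 takes in an existing list of 585 children and "consecutive new referrals to the service (n~43 p/m) across the 18 month recruitment period". It adds: "The waiting period will be divided into thirds and research effort equally extended on each third".
- **Planned proportion.** Section 9.2.1 states: "The proportion receiving physical intervention is anticipated to be around 21% during the follow up time". It gives a 95% CI of 17.45% to 24.55% on 510 children with complete follow-up. The only reference attached is a book of sample size tables.
- **Data.** Section 6(a) requests routine clinic data for the subset seen at endocrine clinics. Appendix 3 does not list dates of referral acceptance, first appointment or treatment start.

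**The concern.** Sections 2 and 6(a) present physical treatment as something reached through the service and its endocrine clinics. On that pathway, the wait that remains after baseline is time in which treatment is unlikely to start, yet it is counted as follow-up. Spreading recruitment effort over thirds of the waiting period balances the sample across the queue. It does not equalise time at risk, and it ensures that remaining wait varies between participants.

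The two-year proportion therefore has no common clinical origin. It does not run from first appointment, because remaining wait differs. It does not run from referral either, because baseline falls at different times after referral. A child first seen late in follow-up would count as untreated in the same way as a child seen early who did not proceed. Services reading the result could take a throughput effect for a clinical one. For predictors, variation in wait that is unrelated to a characteristic would mainly dilute its effect, while variation correlated with it would confound. Observation time after treatment start, needed for research question 3(a), is shortened in the same way.

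**Working it through.** **1. The plan's own figures (Section 9.2.1).**
- Recruitment target: 0.70 × 912 = 638.4, stated 638.
- Completers: 638 × 0.80 = 510.4, stated 510.
- CI for 21%: 0.21 ± 1.96 × √(0.21 × 0.79 / 510) = 0.21 ± 0.0353, or 17.47% to 24.53%. The stated interval is 17.45% to 24.55%, a difference of 0.02 points. The arithmetic is sound; the question is what the 21% measures.

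**2. Implied length of the queue.** Wait = list size / monthly inflow. This assumes a steady list, first come first served, with nobody leaving it.
- Section 9.2.2 rate: 585 / 43 = 13.6 months, 57% of 24 months, leaving 10.4.
- Section 9.2.1 rate: 912 / 18 = 50.7 per month; 585 / 50.7 = 11.5 months, 48% of 24 months, leaving 12.5.

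**3. Room to extend follow-up.** Study period 48 − recruitment 18 − follow-up 24 = 6 months, less than either implied wait.

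**4. Illustration A: 21% is the 24-month risk from first appointment.** Assume a constant rate, no treatment before first appointment, and remaining wait spread evenly over 0 to 13.6 months.
- Rate = −ln(0.79) / 24 = 0.00982 per month. Risk by T2 = 1 − exp(−rate × months left).

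| Third of remaining wait | Mean wait (months) | Months left | Treated by T2 |
|---|---|---|---|
| Short | 2.3 | 21.7 | 19.2% |
| Middle | 6.8 | 17.2 | 15.5% |
| Long | 11.3 | 12.7 | 11.7% |

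- Average 15.5% (about 79 of 510). A child facing the full wait: 9.7%.
- Odds ratio, zero wait against full wait: (0.21 / 0.79) / (0.097 / 0.903) ≈ 2.5, from queue position alone.
- Over both inflow rates and three shapes (constant rate, linear, constant after a 6-month lag), the average is 13.5% to 16.3%, the full-wait figure 5.6% to 11.5%, and the odds ratio 2.0 to 4.5.

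**5. Illustration B: 21% already runs from baseline.** The average stays at 21% by construction. Calibrating a constant rate to the mean time left gives −ln(0.79) / 17.2 = 0.0137 per month.
- Short third: 1 − exp(−0.0137 × 21.7) = 25.7%.
- Middle third: 21.0%.
- Long third: 1 − exp(−0.0137 × 12.7) = 16.0%.

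The level is restored, but the ratio of about 1.6 between the outer thirds remains.

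**The case against.** The strongest reply is that the 21% most naturally runs from baseline, since follow-up in this protocol means the two years after it. That stands. A reader might infer from Illustration A that the true figure is 15.5% and that the stated CI is therefore wrong. The documents do not support that: no section says that the 21% runs from first appointment, and the interval only shows precision at an assumed 21% with 510 children.

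Other points also stand in part:
- The wait is derived; the protocol states no waiting time or throughput.
- It is nowhere stated that treatment cannot start before a first appointment. In Section 9.1.1, first contact could mean contact by the study. Section 9.3.2 puts several steps before baseline, so some children might be seen sooner.
- A constant rate at all ages from 3 to 13 is crude. Section 2 speaks of treatment starting in early puberty, so for the youngest children age rather than the queue may be the limit.
- No section links queue position to child characteristics, so a false predictor is a possibility and not a documented bias.
- Section 7(a) promises appropriate regression models and a later analysis plan, and the 14 explanatory variables are not listed. Waiting time might be among them, so a missing adjustment is not the point here.
- Starting at the waiting list suits a question about referred children (Section 3) that includes those who do not progress through the service (Section 3.2). Making first appointment the sole or lead origin would drop children never seen.

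Section 9.2.2 also promises regular review if service throughput changes. That concerns recruitment and does not equalise time at risk. None of these points removes the unequal time after first appointment.

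**Conclusion.** The concern holds as a matter of time origin and data capture, and should be addressed. Fixed follow-up from a baseline on the waiting list, combined with recruitment across the whole queue, makes time available for treatment after first appointment unequal by design. The implied full wait is about 11.5 to 13.6 months, roughly half of follow-up, under a steady first-come, first-served list.

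The 21% may be right on average if it runs from baseline. The two-year proportion nevertheless depends on remaining wait and understates eventual treatment, because starts after T2 are not counted. The percentages by third and the odds ratios show possible size under assumed rates; they are not estimates from the documents. How far any predictor is affected depends on its correlation with waiting time, which is unknown.

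**What to change.** 1. In Section 9.2.1, state the time origin and basis of the 21%.
2. In Section 6(a) and Appendix 3, provide for dates of referral acceptance, first appointment and treatment start from service records for all participants, not only the endocrine subset.
3. Keep the two-year proportion from baseline, labelled as depending on waiting time.
4. Add cumulative incidence of physical treatment from referral acceptance, with delayed entry at baseline, and from first appointment, both censored at T2.
5. Include waiting time in the predictor model for physical treatment.
6. Report the number of children not yet seen at T2.

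The cost is a small data request, possibly with a consent or ethics step, and some added analysis text. The later part of the cumulative incidence curves will be less precise, because fewer children contribute long follow-up after first appointment. Analysis cannot recover treatment starts after T2. Recruitment and clinical care are unchanged.

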9.2.2 Sampling technique

a) Quantitative study

All children and young people aged 3-13 years when their referral was accepted by the GID service and awaiting a first appointment will be invited to participate in the study. This includes those currently sitting on the waiting list (n=585) and consecutive new referrals to the service (n~43 p/m) across the 18 month recruitment period. The waiting period will be divided into thirds and research effort equally extended on each third. In this way, we shall strive to treat each interval of waiting equally. Our revised strategy will be reviewed regularly and adapted should there be any change in policy towards, or service throughput of, this age group.

b) Qualitative study

Purposive sampling to the qualitative study will be informed by data from the quantitative study. A key aim is to interview CYP who subsequently go on to experience continuing gender dysphoria and progress to physical treatments, as well as CYP whose gender identity issues subsequently resolve and who do not progress to physical treatments. As these outcomes will not be known at baseline, sampling will take account of factors considered to be associated with these outcomes based on current research evidence and clinical knowledge. To address this we will sample equal numbers of CYP who have socially transitioned at baseline and equal numbers who have not socially transitioned at baseline, although we will review this strategy in the light of new evidence emerging over the course of baseline sampling. Across the whole sample we will aim to interview approximately 12 CYP with co-occurring ASD reflecting the large numbers of such CYP referred to GIDS, and approximately 6-8 black and ethnic minority CYP reflecting the UK general population. Sampling will also aim for balance in family socioeconomic status, location of GIDS and assigned gender at birth. Sampling will also be informed by the ongoing analysis of both the quantitative study data and qualitative data on an iterative basis.

9.3 Recruitment

9.3.1 Sample identification

a) Quantitative study

Potential participants will be identified from a list of referrals received at the service. Following a request for specific information, a member of the Trust's informatics team will go through a referral list received at the service to source those aged 13 and under at the time their referral was accepted by GIDS and who are currently awaiting their first appointment. They will not need special permissions as they would routinely access this data.

b) Qualitative study

The quantitative assessments will commence prior to the qualitative study. All families will be asked to consent to be approached for participation in the qualitative study at the point of consent for the quantitative assessments. Consent to being contacted for the qualitative study, at the time of consenting for participation in the quantitative study, will be optional. The research assistants working on the quantitative study will share the details of all participants who consented to be contacted for the qualitative study with the qualitative research associate. A sub-set of families (children and young people and their parents) will be identified and recruited to participate from the consents received, as per the above sampling technique. As capacity to take part in an interview is not necessarily dependent upon age, we will explore whether children and young people display Gillick competence at the time of interview. Those who display such capacity will be asked to provide informed consent.

9.3.2 Consent

It is the responsibility of the Investigator, or person delegated by the Investigator to obtain written informed consent from each participant (or assent from their personal consultee) prior to participation in the trial. The informed consent process will be conducted by the research assistants/research coordinator, who will be GCP trained, suitably qualified and experienced in assessing capacity and will have been delegated this duty by the CI or PI on the delegation log. Participants will be given at least 24 hours to consider participating in their first assessment and given the opportunity to ask any questions. It will be explained to the participant that they are under no obligation to participate in the trial and that they can withdraw at any time during the trial without having to give a reason. For the majority of participants for whom data collection will be carried out remotely and electronically, an econsent procedure will be employed. This will involve participants/ caregivers verbally confirming they are happy to take part in the study and this will be reflected on Red Pill as a tick box for both children and caregivers. For the minority of participants for with whom in-person data collection is carried out, a hard copy of the signed informed consent form will be shared with the participant. The

original signed form will be retained in the investigator site file (ISF) and a copy in the medical/case notes/source documents.

If the PIS and consent form are amended during the trial, participants will be informed of the changes and will be re-consented as appropriate.

a) Quantitative study

Consent will consist of a three-step process. 1) Potential participants (children and young people and their families) will firstly receive a study invitation letter (please see Appendix 6) informing them of the study and inviting them to take part. This letter will, where possible, be included with the child or young person's referral acknowledgement letter sent by the GID service as standard procedure. 2) At least 72 hours after the letter is sent, the child or young person and their family will be contacted by telephone by a member of the GIDS team with responsibility for referrals as part of their duties. The purpose of this telephone call is to highlight the study to potential participants and seek their consent in passing on their contact details to the research team. 3) Should potential participants be happy for their contact details to be forwarded to the research team, a researcher will contact them to share the information sheets, talk through the study and schedule a time for a baseline assessment.

Informed consent will be requested at baseline assessment prior to participation from all caregivers. The majority of assessments will be carried out electronically via Red Pill and guided by the researchers either over the phone or on video call (ie. telemedicine). Consent will be requested and recorded online on the Red Pill database. Caregivers will be re-assessed for capacity to consent verbally by telephone or video calls at follow-up. In a minority of participants, who do not have access to technology or where there are difficulties with technology, we will record consent on paper (at baseline) and conduct assessments in-person.

All children and young people will be asked to assent throughout the study. Under common-law in England those aged 18 years or older are regarded as adults, but we understand that some of our participants may display Gillick competence to consent at a younger age. We have sought guidance on this issue from our sponsor's representative, HRA guidelines, and the research literature in relation to age of consent for minors' participation in research. Although capacity to consent is not dependent on age, these sources displayed a general consensus that individuals aged 16 years or older are likely to be able to consent. In this study, however, we will ask for ethical permission to assent all children and young people for two reasons: 1) only a minority of young people in the study will have reached the age of 16 at the final follow-up assessment, and 2) consenting this small group will require that the

The Tavistock and Portman
NHS Foundation Trust

researcher(s) check all participants' date of births, contact those who are over the age of 16 to assess whether they have capacity to consent, and subsequently contact Red Pill to issue a consent form (if required). As the study aims to recruit 638 families and assess these at three separate time-points, time constraints are likely to make this unfeasible.

Please see Appendix 6 for copies of all information sheets, consent and assent forms for the quantitative arm of the study.

b) Qualitative study

Participants will be invited to partake in an interview following their participation in a baseline assessment. At baseline assessment, participants will be asked whether they agree to be contacted to participate in an interview. An information sheet will be provided to all participants at interview. Informed consent will be required prior commencing all interviews. Please see Appendix 7 for copies of information sheets, consent and assent forms for the qualitative arm of the study.

10 ETHICAL AND REGULATORY CONSIDERATIONS

This research is subject to review by the Health Research Authority for HRA Approval and the NHS Research Ethics Committee for REC Favourable Opinion.

10.1 Assessment and management of risk

Senior clinicians experienced in managing safeguarding issues will provide supervision and training to all research assistants. Research assistants who are recruited to the study will have demonstrated strong empathy skills and, following training, will possess an understanding of the potential difficulties experienced by gender diverse children. In addition, research assistants will receive ongoing supervision regarding their interactions with participants, which will incorporate any feedback received by the team about the conduct of research assistants from participants themselves.

Participants may, at times, become distressed during assessments and/or interviews. Should a participant become distressed during either, they will be asked if they would like to take a break or discontinue the assessment/interview. At the conclusion of each assessment or interview, the researcher will debrief with the participant to check how they are feeling. In the event that a participant

15

The Tavistock and Portman

NHS Foundation Trust

becomes significantly distressed or discloses suicidal intent or another significant event that places them at risk, the researcher will inform the GID clinician on-call via the GID enquiries rota immediately after the assessment/interview. Please see the risk protocol (Appendix 8) for more information.

Interviews, and a minority of assessments, are likely to take place within the family home. We acknowledge that home interviews may pose a potential risk to staff. All staff will be required to wear a portable Identicom safety alarm. This alarm has a panic button that directly alerts both the alarm company, and subsequently, the researcher coordinator/PI or agreed contact, when pressed. All researchers will also be asked to let the research coordinator know when they are entering and leaving the site of an interview.

